## 1.2 Description of ADCT-502

ADCT-502 is an antibody drug conjugate (ADC) composed of an engineered version of the humanized monoclonal antibody trastuzumab, directed against the human HER2 receptor, site-specifically conjugated to SG3199, a pyrrolobenzodiazepine (PBD) dimer cytotoxin, through a protease-cleavable valine-alanine linker. [REDACTED]

ADCT-502 specifically binds to HER2, and once internalized, releases the PBD dimer to allow cross-linking of DNA and eventually trigger cell death. ADCT-502 has demonstrated potent and specific in vitro and in vivo antitumor activity in [REDACTED] with differing levels of HER2 expression.

## 1.3 Nonclinical Efficacy and Toxicology of ADCT-502

*In vitro* studies support a mechanism of action whereby ADCT-502 binds to HER2, internalizes, and releases its cytotoxic payload. In preclinical in vivo xenograft experiments (including patient derived xenograft [PDX] models), ADCT-502 [REDACTED]

[REDACTED] The efficacy of ADCT-502 in these models is due to HER2-mediated delivery of the PBD cytotoxin SG3199.

ADCT-502 [REDACTED]

Additional details may be found in the current ADCT-502 Investigator's Brochure (IB).

## 2 Rationale

### 2.1 Study Rationale and Purpose

Three mAb-based therapies targeting HER2 are currently licensed across 2 indications, namely breast cancer and/or gastric/GE junction cancers. Use of any of these agents is limited to patients whose tumors are defined as HER2 positive, which in this protocol is specified as HER2-high. Until HER2 targeted therapies became available, HER2 expression was associated with worse prognosis compared to patients whose tumors did not over-express HER2.

Consequently, there is unmet medical need in those indications where HER2 is expressed at high levels, but for which the current treatments are not licensed. Also, there is high unmet medical need in breast and gastric/GE junction cancers in which HER2 expression is observed but below the defined thresholds for HER2 targeted therapy.

In addition, high unmet medical need exists in the licensed indications once current HER2 targeted therapy is no longer effective and patients relapse, or which are primary resistant to this therapeutic approach. For example, a substantial number of patients develop resistance to trastuzumab or T-DM1 ([Chung, 2013](#); [Barok, 2011](#)).

Finally, trastuzumab-based regimens are associated with significant side effects, largely because of the cytotoxic chemotherapy component ([Hernández-Blanquisett, 2016](#); [Chung, 2013](#); [Arteaga, 2011](#)). The effects of many of these drugs are short-lived, and a significant proportion of these patients still relapse and die of breast cancer. Thus, promising new approaches are being developed, such as antibodies linked to cytotoxic moieties, to enhance the risk-benefit ratio of drugs.

The mechanism of action and preclinical data of ADCT-502 supports its use in patients with relapsed or refractory metastatic breast and gastric cancer who have been previously treated with trastuzumab/T-DM1. Given the substantial prevalence of HER2 expression in a range of other advanced cancers, including NSCLC, bladder, biliary tract and ovarian cancer, ADCT-502 will be evaluated as an anticancer treatment in patients with such tumor types for which there is published clinical evidence of HER2 expression.

Results of preclinical studies in PDX models suggest that ADCT-502 may have potent clinical activity in both groups of patients, those with HER2-positive/high tumors as well as those with HER2 low-expressing and/or heterogeneous tumors, the latter being a patient population currently not served by approved HER2 targeting agents at all.

### 2.2 Rationale for Study Design

The dose escalation portion of this Phase 1, open-label, dose finding study is designed to establish a safe and tolerated dose of ADCT-502 for further testing in patients with solid tumors expressing HER2 (high and low expressers). Up to nine (9) groups are planned in the expansion portion to further characterize the safety and evaluate preliminary efficacy. As indicated in [Section 4.1](#), the enrollment of the groups is staggered in order to allow for an

evaluation of the therapeutic potential in a limited number of patients with breast and GE cancer prior to exposing patients with other tumor types to ADCT-502.

Part 1 will utilize a modified continual reassessment method (mCRM) to guide dose escalation and estimate the maximum tolerated dose (MTD) and/or determine the recommended dose for expansion (RDE) for ADCT-502. The mCRM and escalation with overdose control (EWOC) enables incorporation of available prior information and updates the model parameters based upon new information about observed dose limiting toxicities (DLT) seen in the clinical study. The dose recommended by the model at any stage of the trial is based on the entire history of all available DLT information from previous cohorts as opposed to only the number of DLTs observed in the last group of patients. Part 2 will utilize the Simon two-stage optimal design with a futility stop and staggered enrollment to minimize exposure of patients when evidence for efficacy is weak.

### 2.3 Starting Dose Justification

The starting dose of ADCT-502 in this study is based on the intravenous (IV) Good Laboratory Practice (GLP) toxicology study with once every 3 weeks dosing. Based on the ADCT-502-related effects observed in this GLP study, [REDACTED]

The starting dose for an ADC is based on the conversion of the HNSTD ([REDACTED] to a Human Equivalent Dose (HED) based on body surface area (BSA) through multiplication with a species specific factor ([REDACTED]), which is followed by division with a standard safety factor of [REDACTED]

### 2.4 Plans and Justification for Provisional Dose Levels

Overall, approximately 10 dose levels are planned. An initial increase of 100% for lower dose levels is foreseen, resulting in provisional dose levels of 30, 60 and 120  $\mu\text{g}/\text{kg}$ . Midstage escalation is somewhat more conservative to account for potential low-grade toxicity to become apparent, with dose level increases of 50%, 33% and 25%, resulting in doses of 180, 240 and 300  $\mu\text{g}/\text{kg}$ . Subsequent levels are determined by a fixed dose increase of 50  $\mu\text{g}/\text{kg}$  (i.e., 300, 350, 400, 450 and 500  $\mu\text{g}/\text{kg}$ ) as the highest dose level to be tested, if allowed by the mCRM with EWOC. The default dosing regimen is once every 3-week dosing. Clinical and pharmacokinetic (PK) data will be reviewed on an ongoing basis and may provide evidence to support interim dose levels. In addition, or as an alternative to decreasing doses to interim dose levels, the dosing interval may be extended (but not shortened), for example, to dosing every 4, 5 or 6 weeks instead of every 3 weeks. Once the dose interval is changed or an intermediate dose not predefined in the mCRM model is used, 3+3 design may be used for future dose escalation. One situation in which such approach may be advantageous is drug accumulation; implementation will need DESC approval (DESC, see [Section 4.6.1](#)) and may affect both ongoing patients as well as new cohorts. Similarly, it is at the discretion of the DESC to modify the dosing regimen that mandates omitting dosing of every n-th cycle, e.g. every 3rd cycle. Note: Scheduled visits will be kept,

except when C2 dosing is skipped; in that case C2D2-D5 would be omitted (respective assessment will not be done). This approach may be beneficial in balancing efficacy and adverse events. The cumulative dose of ADCT-502 in such a revised regimen can only be less than or equal to the cumulative dose of a dose-level that has been tested and found to be safe per mCRM.

### **3 Study Objectives and Endpoints**

#### **3.1 Objectives**

##### **3.1.1 Primary Objectives**

- Evaluate safety, tolerability, and determine the MTD and/or RDE of single agent ADCT-502 in patients with advanced solid tumors with known HER2 status (IHC  $\geq 1+$  or HER2 amplified/mutated) (Part 1).
- Further evaluate safety and tolerability at the dose level determined in Part 1 in patients with advanced solid tumors including breast cancer, lung, gastroesophageal, and bladder cancer or a basket of other solid tumors known to express HER2 (HER2-high or HER2-low status confirmed prospectively for study entry) (Part 2).

##### **3.1.2 Secondary Objectives**

- Evaluate the preliminary antitumor activity of ADCT-502.
- Characterize the PK profile of ADCT-502.
- Determine the immunogenicity of ADCT-502.

#### **3.2 Endpoints**

##### **3.2.1 Primary Endpoints**

- Frequency and severity of DLTs (Part 1 only), adverse events (AEs), serious adverse events (SAEs), laboratory abnormalities, physical examinations, ECOG performance status, vital signs, and 12-lead ECGs.

### 3.2.2 Secondary Endpoints

- Overall Response Rate (ORR), Disease Control Rate (DCR), Duration of Response (DOR), PFS, and OS.
- Determination of PK parameters for ADCT-502 (area under the concentration versus time curve (AUC) of total antibody, (drug to-antibody ratio [DAR]  $\geq 0$ ), PBD-conjugated antibody (DAR  $\geq 1$ ), and free warhead SG3199).
- Anti-drug antibody (ADA) titers to ADCT-502 before, during, and after treatment with ADCT-502.

## 4 Study Design

### 4.1 Overview

This is a first-in-human (FIH) Phase 1, multicenter, open-label study to evaluate the safety, tolerability, PK, pharmacodynamics (PD), immunogenicity, and preliminary antitumor activity of ADCT-502 used as a single agent in patients with advanced solid tumors with documented HER2 expression. The study consists of two parts (see [Figure 1](#)).

During Part 1 (Dose Escalation), patients will receive escalating doses of ADCT-502 according to a mCRM to determine the MTD and/or RDE.

Patients participating in Part 2 (Dose Expansion) will have their HER2 status prospectively measured to be classified as either HER2-high or HER2-low as defined for the study and assigned to 1 of 9 groups as follows:

- Group A: HER2-high breast cancer
- Group B: HER2-low breast cancer
- Group C: HER2-high gastric/GE cancer (and staggered HER2-low)
- Group D: HER2-high bladder cancer (and staggered HER2-low)
- Group E: HER2-high NSCLC (and staggered HER2-low)

- Group F: Basket of 8 HER2-high solid tumor indications (SCLC, CRC, pancreatic, biliary tract, prostate, ovarian, endometrial, or salivary gland)

The proposed indication for Group C (HER2-high gastric/GE cancer) may be exchanged with the indication of Group D or E (HER2-high bladder cancer or NSCLC), or one of the indications from the basket group, depending on emerging data from Part 1.

Simon's 2-Stage design will be used during Part 2. Enrollment will be paused and a futility analysis performed after Stage 1 (see [Section 12.2](#), Interim Analysis [Part 2]). If futility is not triggered, enrollment for that group will continue to Stage 2.

Groups A, B, and C will be opened for enrollment simultaneously. If for one or more of Groups A, B, or C futility is not triggered, Groups D, E, and F will be opened.

If futility for the HER2-high patients enrolled in Stage 1 of Groups C, D, or E is not triggered, enrollment of HER2-low expressing patients in the respective group will be opened.

This recruitment of HER2-low patients in indications of Groups C, D and E is also subject to a Simon 2-stage design.

## **4.2 Patient Selection and Evaluation of HER2 Expression/Amplification/Mutation**

Five (5) types of patients, based on HER2 expression levels and mutations, are selected in this FIH study of ADCT-502:

1. Patients with indications and HER2 expression levels that qualified them for (prior) treatment with trastuzumab and/or ado-trastuzumab emtansine, e.g., HER2 positive BC and HER2 positive G/GE cancer.
2. Patients with BC or G/GE cancer with HER2 expression that is present, but at a level that is below the threshold qualifying them for Item Number 1.
3. Patients with HER2 expression levels equivalent to Item Number 1, but who have a tumor type other than BC or G/GE cancer (NSCLC, small cell lung cancer [SCLC], CRC, bladder, pancreatic, biliary tract, prostate, ovarian, endometrial, and salivary gland cancer).
4. Patients from the same indication list as in Item Number 3, except with HER2 expression levels present but lower than that, i.e. equivalent to expression levels in Item Number 2.
5. Patients with 1 of the 12 indications mentioned in Items 1–4 who have been shown to possess a *HER2* hotspot mutation; they are either classified as HER2-high if a concomitant amplification was demonstrated (or if they fulfill HER2-high criteria as per below definition), otherwise they are classified as HER2-low. Patients with such *HER2* genetic alteration pre-defined prior to study enrollment and not belonging to 1 of the 12 indications may be included in the dose escalation part after sponsor agreement.

HER2 status will be tested by IHC (HercepTest, Dako, Denmark) and scored as 0, 1+, 2+, or 3+, and/or FISH (HER2 FISH pharmDx, Dako). HER2 amplification testing may be performed according to applicable in situ hybridization (ISH) methods as described in the ASCO guidelines (e.g., amplification testing is not limited to FISH). Amplification testing can also be done via NGS (see below).

**A HER2-high patient is defined as IHC 3+, or IHC 2+ with FISH amplification.**

This definition is consistent with the approved indications for trastuzumab and ado-trastuzumab emtansine [T-DM1] (Kadcyla) based therapy.

**A HER2-low patient is defined as IHC 1+, or IHC 2+ without FISH amplification.**

**Note:** patients with IHC 0 / IHC 1+ with amplification is HER2-high for study purposes; a patient with IHC 3+ with negative amplification results is HER2-low for study purposes.

Mutational hotspots indicate selective pressure across a population of tumor samples ([Chang, 2016](#)). Therefore, even if not formally demonstrated for each instance, it is plausible to assume that such mutational hotspots in HER2 signify expression of the protein, at least at HER2-low levels, and thus ADCT-502 should be beneficial as per pre-clinical data in low-expressing HER2 models. Indeed, it was formally demonstrated that *HER2* somatic mutations are being expressed, at the RNA level for a subset of mutations listed in the appendix ([Bose, 2013](#)).

Furthermore, [Mazieres, 2013](#), has published supporting evidence with other HER2 targeting agents in a population with *HER2* mutations; hence, such patients are allowed into the study.

More recently, also HER2 amplification status was shown to be reliably determined by hybridization capture-based NGS methods; e.g., NGS fold change  $> 1.8$  was equivalent to FISH  $> 2.0$  ([Ross, 2017](#)).

Therefore, patients with results available from next generation sequencing (NGS) from a Clinical Laboratory Improvement Amendment (CLIA) certified laboratory will be assigned to these groups as follows:

**For Part 1:**

*HER2* gene amplification irrespective of mutational status: HER2-high.

*HER2* mutated in the absence of amplification: HER2-low. Refer to [Appendix 18.3](#) for genetic changes that constitute a mutation for purposes of this study.

Irrespective of NGS results, *HER2* expression status will be confirmed retrospectively in a central laboratory.

**For Part 2:**

Assignment of HER2-high or –low status via NGS (as described above) must be prospectively confirmed centrally by IHC and FISH (if applicable).

Patients in Part 2 must have their HER2 status measured prospectively for study entry and be classified as either HER2-high or HER2-low as defined for the study.

The different level of scrutiny applied to HER2 testing (historic local vs. prospective central, allowing defined *HER2* mutations as a proxy for HER2 expression during dose escalation) corresponds to the different goals of the two phases of the study: Part 1 being primarily driven to establish a safe dose for expansion, and Part 2 assessing both tolerability as well as initial signs of efficacy.

### **4.3 Number of Patients**

During Part 1, approximately 30 patients may be treated, depending on safety observations and number of dose levels tested.

In Part 2, the total number of patients will be determined by the number of responses for each tumor type stratified by the level of HER2 expression. Initially, 3 groups (Groups A, B, and C) with 13 patients in each group will be enrolled (39 patients). Depending on efficacy signals, up to approximately 248 patients across 9 different groups could be enrolled (i.e., between approximately 39 and 248 patients will be enrolled in Part 2).

The total number of patients will be between approximately 69 and 278.

### **4.4 Duration of Patient Participation**

The duration of each patient's participation will be dependent on individual response to treatment and will include a Screening Period of up to 28 days, Treatment Period, and Follow-up Period. Patients may continue treatment until disease progression or unacceptable toxicity.

All patients will have an EOT visit as soon as possible after decision to discontinue ADCT-502 and prior to initiation of new anticancer treatment. If possible, collection of PK, soluble HER2, and ADA samples will take place at the follow-up visit 12 weeks after the last dose of ADCT-502, unless a new anticancer treatment has been initiated.

All patients will be followed approximately every 12 weeks after the last dose of study drug to collect survival information. Follow-up for survival may continue for up to 2 years after treatment discontinuation.

Any patients who discontinue treatment for any reason other than disease progression will continue to be followed by radiographic examination every 12 weeks until disease progression or initiation of new anticancer treatment.

The duration of the study participation for each patient is defined as the time from the date of

signed written informed consent through the completion of the follow-up period, or withdrawal of consent.

#### **4.5 Duration of Study**

Study duration will be dependent on overall patient tolerability and response to treatment. It is anticipated that the entire study (Part 1 and Part 2) could be approximately 3 years from first patient treated to last patient completed.

#### **4.6 Description of Dose Escalation Process**

Each cohort will consist of 2 patients. There will be a 24-hour observation before enrolling the second patient at Dose Level 1. The DLT observation period at each dose level is 1 cycle (3 weeks), after which it will be determined whether to escalate to the next dose level, stay at the current dose level, or de-escalate to the previous dose level for the next cohort.

There will be no de-escalation from Dose Level 1. Intrapatient dose escalation is not permitted.

Dose escalation is not permitted unless two or more patients have complete DLT information through the first cycle in any given dose level. Dose escalation will be determined by using a mCRM with a target DLT rate of 30% and an equivalence interval of 20% to 35%, and with dose escalation-with-overdose-control (EWOC) and no dose skipping.

The mCRM will be implemented in Part 1 under the oversight of a Dose Escalation Steering Committee (DESC). The DESC will confirm each escalating dose level after reviewing all available safety data. PK data from patients in that dose level and prior dose levels may also inform decision making. The DESC may halt dose escalation prior to determining the MTD based on emerging PK, PD, toxicity, or response data.

Additional patients may be included at any dose level to further assess the safety and tolerability if at least 1 patient in the study has achieved a partial response or better, or if further evaluation of PK or PD data is deemed necessary by the DESC to determine the RDE.

Furthermore, to better understand the potential efficacy of ADCT-502 in an indication approved for treatment with HER2 targeted antibodies, up to 3 additional breast cancer patients who have previously been treated with an approved HER2 targeted therapy may be enrolled per cohort at given dose levels  $\geq 60 \mu\text{g/kg}$  determined by the mCRM model to be safe.

Dose escalation will be stopped after the mCRM has assigned 3 cohorts consecutively to the same dose level.

If the MTD is not reached, the recommended dose(s) and schedule(s) for expansion (RDE) will be determined.

Once the Part 2 RDE(s) is/are determined, patients receiving lower or higher dose levels of ADCT-502 enrolled in part 1 may be offered continued treatment at the RDE(s).

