#### 4.6.1 Safety Oversight by the Dose Escalation Steering Committee

A DESC comprised of ADC Therapeutics and the investigators will review patient safety on an ongoing basis during Part 1 to determine if the dose escalation schedule prescribed by the mCRM warrants modification. In addition to safety observations, PK and/or PD data may also inform DESC decision making. Intermediate doses or extended dosing intervals may be assigned after agreement between ADC Therapeutics and the investigators. The DESC will continue to provide oversight during Part 2. No formal Data Safety Monitoring Board (DSMB) will be used.

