## 18.4 Appendix: Modified Continual Reassessment Method of Dose Escalation

### 18.4.1 Overview

Planned dose levels for ADCT-502 are shown below in [Table 9](#). Dose escalation will be conducted according to a mCRM, with dose EWOC and no dose skipping.

A recommendation to escalate, stay, or deescalate the dose level for the next 2 patient cohorts will be made according to the planned dose scheme in [Table 9](#).

The study will be continuously monitored for safety and early stopping for successfully identifying the MTD. Dose escalation will be stopped when 3 cohorts are consecutively assigned to the same dose level, which will be identified as the MTD.

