### 18.4.2 Model and Priors

Dose escalation in this study will be conducted using the mCRM.

For each dose,  $d = 1, \dots, n$ , we model the binary outcome of non-DLT, or a DLT.

The log odds of a DLT are modeled as

$$\theta_d = \log\left(\frac{\pi_{DLT}}{1 - \pi_{DLT}}\right)$$

with a 2-parameter model

$$\theta_d = \alpha + \exp(\beta) \log(d_i / d^*)$$

where  $d^*$  is the reference dose, which is used to standardize the dose  $d_i$  and allows for the interpretation of  $\alpha$  as the odds of a DLT at  $d^*$ .  $\exp(\beta)$  is positive, ensuring a monotonically increasing dose-toxicity relationship.

[Neuenschwander, 2008](#) placed a bivariate lognormal prior on the two parameters and proposed eliciting information on the risk of DLT at two (2) or more doses to obtain prior means and variances. Several articles have examined the specification of priors. When there are no previous historical clinical data available, it is possible to use uninformative prior. For this purpose, the above model can be re-parametrized in terms of  $(\rho_0, \gamma)$ , where  $\rho_0$  is the probability of a DLT at the starting dose  $d_1$  and  $\gamma$  is the MTD, the dose expected to produce DLT at 0.3 probability in this study, with

$$\gamma = \exp(-\beta) * (\log(\theta_d) - \log(1 - \theta_d) - \alpha)$$

and placing the following independent prior distributions on the parameters.

$$\rho_0 \sim \text{Uniform}(0, 0.30)$$

$$\gamma \sim \text{Uniform}(d_1, d_n).$$

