### 18.4.3 Dose Escalation Rule and Choice of Cohort Size

Dose escalation will begin with 2 patients enrolled at the initial starting dose. The cohort size is 2, which means that 2 patients will be assigned to escalate to the next dose level, de-escalate to the prior dose level, or, stay at the current dose level.

On the completion of each cohort (i.e., 2 patients treated and assessed for DLT after 1-cycle), the posterior distributions of  $\theta(d)$  are summarized for each dose level by the probabilities of under-dosing, targeted toxicity, or excessive/unacceptable toxicity. These 3 probabilities are defined as:

$$\text{Under-dosing: } \theta_d \in (0, 0.20)$$

$$\text{Targeted Toxicity: } \theta_d \in [0.20, 0.35]$$

$$\text{Excessive or Unacceptable Toxicity: } \theta_d \in (0.35, 1]$$

The dose which maximizes the probability of targeted toxicity while controlling the probability of excessive or unacceptable toxicity to  $\leq 25\%$  will be recommended for the next cohort of 2 patients. The model has the flexibility for a larger cohort size if additional patient are available.

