#### **18.4.4.1 Safety Monitoring**

[figure not shown]
The lowest dose (the initial starting dose) will be considered unsafe if the probability of excessive or unacceptable toxicity is  $> 25\%$ . The trial will stop, and no MTD found, if the lowest dose is considered unsafe (hence all doses are considered unsafe).

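### After some DLT patterns none of the three listed dose moves meets the plan's own 25% overdose limit, and no sentence says which rule prevails

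*Protocol*

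**What the plan says.** Three places (Synopsis, Part 1; Protocol 4.6; Protocol 18.4.3) describe the next cohort's dose as a choice of three moves. Protocol 4.6 offers the next level up, "stay at the current dose level, or de-escalate to the previous dose level for the next cohort". Protocol 18.4.3 has the same list, ending "de-escalate to the prior dose level, or, stay at the current dose level".

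Protocol 18.4.3 then gives the model rule for the same cohort: "The dose which maximizes the probability of targeted toxicity while controlling the probability of excessive or unacceptable toxicity to" 25% or less is recommended. Excessive means a DLT rate above 0.35; the target interval is 0.20 to 0.35.

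Other text bears on which rule leads:
- Protocol 2.2: "The dose recommended by the model at any stage of the trial is based on the entire history of all available DLT information" from earlier cohorts.
- Protocol 18.4.1: "A recommendation to escalate, stay, or deescalate the dose level for the next 2 patient cohorts will be made", with no step size.
- Protocol 4.6: escalation ends once the mCRM has assigned three cohorts in a row to one level. Dose skipping is ruled out, but no direction is given.
- Protocol 4.6.1: the DESC reviews safety "to determine if the dose escalation schedule prescribed by the mCRM warrants modification".
- Protocol 18.4.4.1: "The trial will stop, and no MTD found, if the lowest dose is considered unsafe".

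None of these covers the case where the previous level also exceeds 25%.

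**The concern.** The 25% limit is the plan's stated overdose control. In the model the DLT rate rises with dose, so the probability of exceeding 0.35 rises with dose too. If the previous level is already above 25%, staying or escalating is at least as bad, and all three listed moves fail. The model's own choice is then two or more levels down, which the list does not offer and a two-way reading of the skipping ban would forbid. A first-in-human escalation rule should give one answer when toxicity appears. If sites followed one rule and the simulations in 18.4.5 followed the other, the reported operating characteristics would not describe the trial as run.

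**Working it through.** The documents give no posterior probabilities or decision table to reproduce, and the operating-characteristic figures are not in our copy. The check therefore rebuilds the printed model.

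**Inputs.** Doses from Table 9: 30, 60, 120, 150, 180, 210, 240, 300, 350, 400, 450, 500 µg/kg. Cohorts of 2. Protocol 18.4.2 specifies the prior by "placing the following independent prior distributions on the parameters": rho0, the DLT probability at 30 µg/kg, is Uniform(0, 0.30), and gamma, the dose with DLT probability 0.30, is Uniform(30, 500).

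**Model.** Writing the two-parameter logistic in terms of (rho0, gamma):

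logit p(d) = logit(rho0) + [logit(0.30) − logit(rho0)] × log(d/30) / log(gamma/30)

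The printed expression for gamma is not transformed back from log dose. As a sensitivity reading the last factor is replaced by (d − 30)/(gamma − 30), called linear below. Posteriors are computed on a 500 × 500 grid.

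**Conflict patterns.** Linear results are in brackets.

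| DLTs so far | P(rate > 0.35), current level | P(rate > 0.35), previous level | Model picks |
|---|---|---|---|
| A: 0/2 at 30, 1/2 at 60, 2/2 at 120 | 0.547 (0.686) | 0.320 (0.356) at 60 | 30 |
| B: 0/2 at 30, 0/2 at 60, 1/2 at 120, 2/2 at 150 | 0.473 (0.661) | 0.398 (0.551) at 120 | 60 |
| 0/2 at 30, 60 and 120, 1/2 at 150, 2/2 at 180 | 0.364 (0.577) | 0.290 (0.455) at 150 | 120 |

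At the model's pick the probability is 0, 0.058 (0.033) and 0.188 (0.233). Under both readings the model permits each one-level escalation on the way, so the patterns are reachable.

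**Patterns without conflict.** Previous-level values after clean lower levels:
- 1/2 at 120, then 1/2 at 150: 0.126 (0.143) at 120.
- 1/2 at 60, then 1/2 at 120: 0.030 (0.017) at 60.
- A single 2/2 at 150: 0.157 (0.225) at 120.

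**Chance of A and B under Scenario 1** (true rates 0.10, 0.17, 0.30, 0.38 at the first four levels):
- A: 0.9² × 2(0.17)(0.83) × 0.3² = 0.021
- B: 0.9² × 0.83² × 2(0.3)(0.7) × 0.38² = 0.034

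**Whole trial.** There were 8,000 simulated trials per scenario. Assumptions: one-level rule applied mechanically, no DESC action, a cap of 30 patients (the protocol says approximately 30), and a stop after three consecutive cohorts at one level.

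| Scenario | At least one cohort above the limit: log dose | Linear |
|---|---|---|
| 1 | 28.5% | 29.4% |
| 2 | 1.4% | 16.9% |
| 3 | 0.3% | 4.2% |
| 4 | 5.7% | 15.8% |
| 5 | 3.9% | 9.3% |

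When the model's dose is used going down, the figure is 0% throughout. A separate enumeration of all paths to nine cohorts, on a coarser grid, gives about 31%, 1.5%, 0.3%, 6% and 4% under log dose (linear 30%, 10%, 2%, 14%, 8%). With gamma uniform on log dose instead, it gives 16%, 4%, 2%, 8% and 5%.

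**Average effect, one-level rule against model dose.**
- Scenario 1, DLTs per trial: 6.47 − 6.26 = 0.21 (6.17 − 5.91 = 0.26).
- Scenario 1, patients at a true rate above 35%: 46.4% against 44.9% (42.7% against 41.6%).
- Scenarios 2 to 5: DLTs per trial differ by 0.04 or less.
- Scenario 1, true 30% dose selected: 35.8% against 34.8% (43.4% against 40.9%), so the one-level rule does slightly better here.

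**Lowest-dose stop.** The prior caps the rate at 30 µg/kg at 0.30, so P(rate > 0.35) there is always 0. The stop in 18.4.4.1 cannot resolve the conflict. For the same reason an admissible lower dose always exists.

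**The case against.** The strongest reply is that the model plainly leads. The mCRM assigns cohorts and prescribes the schedule, the extra breast cancer patients in 4.6 enter only at levels the model finds safe, and 18.4.3 says which dose is recommended. On that view the three-move list only names directions. This has force, and it is probably what was intended. It does not close the point: 18.4.3 prints the specific one-level step beside the 25% rule, and no sentence ranks the two.

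The reply on harm largely stands. Under Scenario 1, the one-level move on pattern A goes to 60 µg/kg (true rate 0.17) and on B to 120 µg/kg (0.30, the true target dose). Of the Scenario 1 cohorts above the limit, 57% (linear 71%) are at a true rate above 35%. In Scenarios 2 to 5 the share is 0% under log dose and at most 13% under linear. Such cohorts hold about 3.7% of Scenario 1 patients under log dose. The DESC can also modify the schedule, halt escalation or assign intermediate doses.

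A reader might infer that these breaches typically follow a run of DLTs. Three or more DLTs in the last four patients precede 81 to 92% of conflicts under log dose but only 17 to 69% under linear, so that does not hold generally. Nor do DLTs at two adjacent levels always create a conflict, as the patterns without conflict show.

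**Conclusion.** The inconsistency is real and minor. After some reachable DLT patterns the listed moves offer no dose within the 25% limit, and the protocol does not say what then happens. Read literally and without DESC action, the one-level wording would breach the limit in roughly 30% of Scenario 1 trials and in 0.3 to 6% (linear 4 to 17%) in the other scenarios. The average cost is about 0.2 to 0.3 DLTs per trial in Scenario 1 and near nil elsewhere.

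These figures rest on the prior as printed, cohorts of exactly 2 and mechanical application. Outside Scenario 1 they depend heavily on how 18.4.2 is read. The existence of the conflict does not: patterns A and B breach the limit under both readings.

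A reader might go further and infer that the plan knowingly doses above its own limit, or that the DESC must be barred from doing so. The documents do not support either. Much of the text favours the model, and limiting the DESC's judgement is a separate preference that resolving the wording does not require.

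**What to change.** In the Synopsis (Part 1), Protocol 4.6 and Protocol 18.4.3, state that one-level steps and the ban on dose skipping apply to escalation only, and that de-escalation goes to the model-recommended dose meeting the 25% limit, even if that is more than one level down. Confirm that the simulations in 18.4.5 used this rule, and rerun them if not.

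The cost is one sentence in three places and a check of the simulation code, with no extra patients. The downside is a chance of selecting the true 30% dose in Scenario 1 that is lower by about 1 point (35.8 − 34.8) to 2.5 points (43.4 − 40.9).
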